1.1. Background and rationale

Vascular access surveillance by flow volume measurements with dilution techniques during dialysis sessions is the standard of care in the Netherlands. However, there is a large practice variation in surveillance frequency and the threshold to trigger referral for vascular access intervention.

Combined with the limited evidence base supporting the use of access surveillance, this variation in protocols indicates the need for further studies to determine the most effective method for follow-up of the vascular access for hemodialysis.

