2.1. Trial design

It is a double-blind, multicenter randomized controlled trial with a superiority framework and a 1:1 individual participant treatment allocation ratio over two study arms. In the intervention group, only symptomatic vascular access stenosis detected by clinical monitoring are treated, whereas in the comparison group asymptomatic stenosis detected by surveillance are treated as well (current standard of care in the Netherlands). Prevalent hemodialysis patients with a functional arteriovenous vascular access are eligible to participate in the trial. Patients will be followed up for a minimum of 2 years and a maximum of 3 years (follow up will end for all participants when the last included patient has reached a 2 year follow-up period) and will be censored when their mode of renal replacement therapy is changed to kidney transplantation, peritoneal dialysis, or conservative treatment.

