2.2. Randomization

Patients will be randomized using a 1:1 individual participant treatment allocation ratio. The data management center will generate the treatment allocation sequence by a random number producing algorithm on a computer. Randomization will be stratified by treatment center and for vascular access type (graft vs fistula). The study coordinator will enroll participants and will be informed of treatment assignment through an online service provided by the data management center.

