2.4. Framework

Superiority framework. The intervention group will be compared to the control group. Analyses will be stratified for treatment center and for vascular access type (graft vs fistula). Every effort is made to establish eligibility of participants prior to randomization; no withdrawals due to ineligibility are allowed and the analyses include all participants enrolled. The primary analysis will be on the intention to treat population (i.e. no participants are withdrawn from analysis for lack of adherence to treatment allocation); exploratory on-treatment analyses will be performed. A comparison of included and excluded patients is done to provide insight into the external validity of the clinical trial. Every effort is made to avoid missing data, including assistance from dialysis nurses in obtaining patient-reported outcome measures during dialysis sessions. Primary outcome data are not expected to be missing, as interventions on vascular access will be reported in the patients' medical files. We expect no loss to follow-up in the study participants since they are observed three times per week in the dialysis unit. Patient-reported outcomes will be analysed using generalized estimating equations that allow for missing data. Other missing data will be handled by using 5 imputation cycles with regression methods. Outliers will not be removed from the analysis unless the data can clearly be shown to be erroneous.

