Cerebrovascular disease	%	N	%	N	...
Peripheral arterial disease		N		N	...
No	%	N	%	N	
Rutherford stage 1-3	%	N	%	N	
Rutherford stage 4-6	%	N	%	N	
Vascular access		N		N	...
Fistula	%	N	%	N	...
Radiocephalic	%	N	%	N	
Brachiocephalic	%	N	%	N	
Brachiobasilic	%	N	%	N	
Graft	%	N	%	N	

Table 2A: Trial screening and enrollment log

	Prevalent hemodialysis patients	
	N	%
Total		
Exclusion criteria		
Home hemodialysis		
Central venous catheter		
Informed consent not possible		
Planned kidney transplantation < 6 months		
Life expectancy < 6 months		
Transfer to another dialysis unit <6 months		
Enrolled in another vascular access trial		
Vascular access thrombosis in the past year		
Vascular access flow <500 mL/min		
Planned vascular access-related intervention		
Vascular access not functional ^a		
Multiple outflow veins in cannulation zone		
Total study candidates		
No informed consent		
Unwilling to participate in trials		
Feeling insecure with blind flow measurements		
Total participants		

Table 2B: Comparison of enrolled patients with unselected hemodialysis population - Baseline characteristics

	Unselected population (N=...)		Enrolled patients (N=...)		P
Sex (male)	%	N	%	N	...
Age (years)	Mean \pm SD	N	Mean \pm SD	N	...
Body mass index (kg/m ²)	Mean \pm SD	N	Mean \pm SD	N	...
Cause of end-stage renal disease		N		N	...
Diabetes	%	N	%	N	
Vascular/hypertension	%	N	%	N	
Glomerulonephritis	%	N	%	N	
Polycystic kidney disease	%	N	%	N	
Interstitial nephritis	%	N	%	N	
Congenital/hereditary	%	N	%	N	
Systemic disease	%	N	%	N	
Other	%	N	%	N	
Unknown	%	N	%	N	
Comorbidities					
Diabetes mellitus	%	N	%	N	...
Ischemic cardiac disease	%	N	%	N	...
Heart failure	%	N	%	N	...
Cerebrovascular disease	%	N	%	N	...
Peripheral arterial disease	%	N	%	N	...
Chronic pulmonary disease	%	N	%	N	...
Active malignancy	%	N	%	N	...
Psychiatric disease	%	N	%	N	...
Time on hemodialysis (months)	Median \pm IQR	N	Median \pm IQR	N	...
Vascular access type		N		N	...
Arteriovenous fistula	%	N	%	N	
Arteriovenous graft	%	N	%	N	

Patients with home hemodialysis and central venous catheters are excluded.

Statistical analysis: Chi squared tests for categorical variables, Student t-test for continuous variables with normal distribution, and Mann-Whitney U-test for continuous variables deviating from normal distribution

Table 2C: Comparison of enrolled patients with unselected hemodialysis population - Vascular-access related interventions and serious adverse events

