	Unselected population (... patient-years)	Enrolled population (...patient-years)	Event rate ratio (95% CI)	P
Interventions for flow dysfunction	N	N	... (....)	...
Percutaneous interventions	N	N	... (....)	...
Balloon angioplasty without stent	N	N	... (....)	...
Balloon angioplasty with stent	N	N	... (....)	...
Percutaneous thrombectomy	N	N	... (....)	...
Surgical interventions	N	N	... (....)	...
Open thrombectomy	N	N	... (....)	...
Patch angioplasty	N	N	... (....)	...
Revision of anastomosis	N	N	... (....)	...
New arteriovenous fistula	N	N	... (....)	...
New arteriovenous graft	N	N	... (....)	...
Ligation of arteriovenous fistula	N	N	... (....)	...
Ligation of arteriovenous graft	N	N	... (....)	...
Central venous catheter interventions	N	N	... (....)	...
Catheter insertion	N	N	... (....)	...
Guidewire exchange	N	N	... (....)	...
Catheter removal	N	N	... (....)	...
Other vascular access interventions	N	N	... (....)	...
Repair (pseudo)aneurysm	N	N	... (....)	...
Ligation of accessory vein	N	N	... (....)	...
Embolisation of accessory vein	N	N	... (....)	...
Superficialisation	N	N	... (....)	...
Distal revision and interval ligation	N	N	... (....)	...
Proximalisation of arterial inflow	N	N	... (....)	...
Revision using distal inflow	N	N	... (....)	...
Banding	N	N	... (....)	...
Serious adverse events				
Thrombosis	N	N	... (....)	...
Access abandonment	N	N	... (....)	...

Statistical analysis: Poisson test with time as offset variable.

Figure 2D: Comparison of enrolled patients with unselected hemodialysis population - Survival

Kaplan-Meier survival curve of unselected hemodialysis population and enrolled patients

Statistical analysis: Log rank test

Figure 2E: Patient allocation to study groups

X-axis: time (1-1095 days)

Y-axis: patients (N=375)

The grid is filled with colors: red when allocated to the monitoring group, blue when allocated to the surveillance group, and grey after the end of the study (different shades of grey may be considered for different reasons to end study participation)

Patients will be ordered according the time of shifting between groups to facilitate interpretation (with patients who remained in the monitoring group the entire study duration at the top of the grid, and patients who remained in the surveillance group the entire study duration at the bottom of the grid)

Table 2F: Vascular access dysfunction detected by monitoring and surveillance - Available measurements

	Monitoring		Surveillance	
	N	Follow-up	N	Follow-up

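### Table 2C tests the enrolled patients, pooled over both arms, against an unselected population, so part of any treatment effect is confounded with patient selection

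*SAP*

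**What the plan says.** Section 2.4 states the purpose: "A comparison of included and excluded patients is done to provide insight into the external validity of the clinical trial". In section 6, Tables 2B and 2C and Figure 2D compare enrolled patients with a wider haemodialysis population. Table 2C does so for access interventions, thrombosis and access abandonment: "Comparison of enrolled patients with unselected hemodialysis population - Vascular-access related interventions and serious adverse events". Its shell has one column for the unselected population and one for the enrolled population, each headed by patient-years, followed by an event rate ratio with 95% CI and a P value. The note reads "Statistical analysis: Poisson test with time as offset variable". It names no arm term or other covariate.

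On allocation, section 2.2 says "Patients will be randomized using a 1:1 individual participant treatment allocation ratio". On the strategies, section 2.1 says "In the intervention group, only symptomatic vascular access stenosis detected by clinical monitoring are treated". The other arm also has silent stenoses treated when flow measurement finds them, which the same section describes as usual Dutch practice. Section 1.1 agrees: "Vascular access surveillance by flow volume measurements with dilution techniques during dialysis sessions is the standard of care in the Netherlands".

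The SAP does not define the unselected population by source, period or care. Section 2.4 speaks of excluded patients, and section 4.1 of patients not included in the trial, who are kept in a screening log.

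**The concern.** The question for external validity is whether the entry criteria (access flow of at least 500 mL/min, a functional access, no thrombosis in the past year, no planned intervention) select patients whose access behaves differently from that of the wider population. To answer it from event rates, both groups should be under similar care. Roughly half of the enrolled time in Table 2C is instead under the strategy being tested, and the rows are largely the intervention types of the primary outcome. If monitoring lowers the intervention rate, the enrolled column falls even when participants are perfectly typical. If participants are at higher risk, the fall can hide it. Thrombosis and abandonment are affected in the same way, possibly in the opposite direction.

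What is at stake is how the result is read. In the case the trial hopes for, a reader of Table 2C could conclude that participants were an unusually low-intervention group and discount the finding for that reason.

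**Working it through.** **Inputs.** From SAP section 2.3: 1.77 interventions per patient-year in the Netherlands; target decrease 0.25; 828 patient-years in total, 414 per arm; 80% power; two-sided alpha 0.05. From section 2.2: 1:1 allocation. Assumed, because the SAP does not say: the unselected population is under usual surveillance care at 1.77 per year, and its patient-years are varied below.

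**The plan's own figure first.** Monitoring rate 1.77 − 0.25 = 1.52. Patient-years per arm for a Poisson rate-difference z-test:

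(1.960 + 0.842)² × (1.77 + 1.52) / 0.25² = 413.2, against 414 stated. It reproduces.

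**Expected Table 2C ratio with no selection.** With s the monitoring share of enrolled person-time, the pooled rate is s × 1.52 + (1 − s) × 1.77.

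| s | Pooled rate | Ratio to 1.77 |
|---|---|---|
| 0.40 | 1.670 | 0.944 |
| 0.50 | 1.645 | 0.929 |
| 0.60 | 1.620 | 0.915 |

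The range is shown because participants can shift between groups (Figure 2E, Table 2L), so one half is only approximate. The arm-to-arm ratio would be 1.52 / 1.77 = 0.859, so at s = 0.5 about half of the treatment effect enters Table 2C.

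**Larger effects.** Section 2.3 expects the minimal clinically relevant difference to exceed 0.25. At s = 0.5, a difference of 0.50 gives (1.77 − 0.25) / 1.77 = 0.859, and 0.75 gives (1.77 − 0.375) / 1.77 = 0.788.

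**Masking.** If participants truly had 10% more interventions than the unselected population under the same care, and monitoring reduced their rate in the same proportion, the table would show 1.10 × 0.929 = 1.02.

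**Significance.** With 828 enrolled patient-years, s = 0.5 and PY unselected patient-years, z = 0.125 / √(1.645/828 + 1.77/PY). At PY = 828, |z| = 1.95 (p about 0.05). The chance that the test is significant at 0.05 although there is no selection:

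| Assumed PY | 414 | 828 | 1,656 | 3,000 | 10,000 |
|---|---|---|---|---|---|
| Probability | 35% | 49% | 62% | 69% | 77% |

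These treat the counts as Poisson, as the table note does.

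**With the surveillance arm only.** The expected no-selection ratio is 1.77 / 1.77 = 1.00.

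**The case against.** A good deal can be said for the plan. Table 2C is descriptive and sits among the study-progress tables, next to the screening log (Table 2A) and the baseline comparison (Table 2B), which show selection directly and are not touched by pooling the arms. Tables 3A and 4A already give the same intervention types, thrombosis and abandonment by arm with patient-years, so a reader could set the surveillance counts beside the unselected column. The rate of 1.77 covers all access interventions, and Table 2C has no such row, so 0.93 is the expected shift in a total that the table does not print; individual rows could move more or less. The entry criteria plausibly select lower-risk access, which makes masked selection towards higher risk the less likely case. All of this stands. It limits the weight of the point, but the ratio and P value that the table does print still use the pooled column.

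Four stronger readings are tempting, and the SAP does not support them:

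- *The trial's treatment effect is reported as a selection effect.* The SAP offers only insight into external validity, and about half of the effect enters the ratio, mixed with any real selection. Confounding is the accurate word.
- *The surveillance arm receives the same care as non-participants.* Section 1.1 reports large variation in surveillance frequency and referral threshold, whereas the trial fixes monthly measurement (section 2.7) and 500 mL/min (section 3.2.1). Participants can also change group, so surveillance time may follow monitoring time. The arm is the closest match, not an identical one.
- *The tests compare overlapping groups.* That follows only if the unselected population contains participants, which the SAP does not say. What is shown is a difference in wording between section 2.4 and the tables.
- *The table will show a false significant difference.* That depends on unselected follow-up that is not given.

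**Conclusion.** The point holds as a confounding problem in one descriptive table. As laid out, Table 2C cannot separate patient selection from treatment effect, and nothing in the SAP restricts its enrolled column to the surveillance arm. At the SAP's target effect the distortion of an all-intervention ratio is about 7% (0.93 instead of 1.00), and it grows with the treatment effect. This rests on three assumptions: the unselected population is under usual surveillance care at about 1.77 per year (inferred from sections 1.1 and 2.1, not stated); 40% to 60% of enrolled time is under monitoring; and there is no selection. If the unselected group includes participants, the distortion is diluted but not removed. Figure 2D also shows enrolled patients as one group, but no effect on survival is assumed in the SAP, so no size can be given there. Table 2B uses baseline data and is not affected by pooling. The primary analysis is untouched.

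**What to change.** 1. In Table 2C, split the enrolled column into monitoring and surveillance, assigning person-time and events by the same allocation rule as Tables 3A and 4A.
2. Compute the rate ratio, CI and P value against the unselected population for the surveillance patient-years only. Show the monitoring column descriptively, without a test.
3. Add a note that the surveillance arm is the closest available match to usual care and not an identical one, because surveillance practice varies and participants can shift between groups.
4. Reconcile the excluded patients of section 2.4 with the unselected population of Tables 2B and 2C and Figure 2D: state source, period and usual care. If that population contains participants, remove them before any two-sample test.

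The cost is table-shell and SAP wording; no new data are needed. The downside is precision, since about half of the enrolled patient-years leave the tested contrast. Against an assumed 2,000 unselected patient-years, the standard error of the log ratio rises from √(1/(1.645 × 828) + 1/(1.77 × 2,000)) = 0.032 to √(1/(1.77 × 414) + 1/(1.77 × 2,000)) = 0.041.

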2.3. Sample size

Sample sizes were estimated for the number of interventions required for each patient-year of dialysis treatment (i.e. the primary outcome), which will be analysed using a general linear model with Poisson distribution and time as off-set variable. In the FLOW project, we aim to detect a difference in the intervention rate of 0.25 per year between study groups in a superiority analysis. This difference is associated with an economically relevant effect of saving approximately 1 million euros per year at a 75% de-implementation rate. The minimal clinically relevant difference in the intervention rate remains to be defined for this core outcome measure, but will likely be greater than 0.25 per year. In the Netherlands, the access-related intervention rate in hemodialysis patients with arteriovenous fistulas and grafts was 1.56 and 3.30 per year, respectively, in a retrospective observation cohort study in 10 dialysis units. As the distribution between fistulas and grafts is approximately 8:1, these figures amount to an average of 1.77 interventions per patient-year in the Netherlands. Since the study includes young hemodialysis patients waiting for kidney transplantation and old hemodialysis patients with limited life expectancy, 20% of participants are expected to leave the study per year before completing the follow-up period. A total follow-up time of 828 patient-years (414 patient-years in each treatment arm) achieves 80% power to detect a 0.25 decrease in the number of interventions per patient-year between the study groups using a two-sided, large-samples z-test of the Poisson event-rate difference at a significance level of 0.05. With a standard follow-up of 2 years and a drop-out rate of 20% per year, this would require a sample size of 518 patients. Implementing a variable follow-up time of a minimum of 2 years and a maximum of 3 years is expected to result in 162 additional patient-years. This corresponds to 101 patients with 2-years of follow-up and a drop-out rate of 20% per year, and therefore leads to a new sample size estimation of 417 patients. An interim analysis for safety requires a sample size of 144 patients (72 in each treatment arm) contributing 1 year of follow-up with an expected event rate of 0.5 events per patient-year to show non-inferiority with regards to access-related serious adverse events at a margin of 0.5 events per patient-year with a power of 90%.

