5.1. Outcome definitions

5.1.1. Primary outcome

The primary outcome will be defined as the number of interventions required for each patient-year of hemodialysis treatment (number of interventions per patient-year). This core outcome measure was defined in an international consensus workshop including patients, clinicians, researchers, policy makers and industry representatives, and includes all percutaneous access interventions (including central venous catheter placement, removal and guidewire exchange, angioplasty, stent placement, percutaneous thrombectomy) and surgical access procedures (including subsequent access placements if the current access failed, and surgical revisions to promote maturation or maintain long-term patency, including open thrombectomy). Interventions that are done under general anesthesia or that require hospital admission of more than one day are scored as major interventions, whereas interventions under local or locoregional anesthesia as day-case of office procedures are scored as minor interventions. These interventions correspond to grade 3A and 3B surgical complications in the Clavien-Dindo classification (30). Access-related complications that are resolved using conservative or pharmacological treatment are not considered as interventions.

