Statistical analysis (intention to treat population): general linear mixed effect model with Poisson distribution and identity link, and with time as off-set variable. The outcome will be expressed as a ratio (exponential of β_1) of events (number of interventions) per 1 unit increase of exposure time between both groups. A random intercept for each individual participant will be estimated to account for dependence of observations. Expected counts will be plotted against observed counts to check whether the distribution of counts follow a Poisson distribution. Furthermore, the Pearson dispersion statistic will be assessed to check whether there is equidispersion of the variance compared to the mean. In case of overdispersion of the data, a quasi-Poisson model or negative binomial model will be performed.

Stratification: study site and vascular access type (fistula / graft).

Subgroup analysis: vascular access type (fistula / graft).

Sensitivity analysis:

- Major interventions counting twice (see Table 3a-2)
- Exclusion of patients with interventions with technical failure (see Table 7A)
- Exclusion of patients with interventions with clinical failure (see Table 7A)

Table 3B: Characteristics of vascular access interventions

	Monitoring (N=...)	Surveillance (N=...)	P
Indication			
Clinical indicators of flow dysfunction ^a	%	%	...
Physical examination			
Weak or discontinuous thrill	%	%	...
High pitched or discontinuous bruit	%	%	...
Hyperpulsatile vascular access	%	%	...
Weak vascular access	%	%	...
No thrill or bruit	%	%	...
Recurrent problems during dialysis			
Inability to achieve target blood flow	%	%	...
New cannulation problems	%	%	...
Prolonged bleeding	%	%	...
Unexplained fall in dialysis efficiency	%	%	...
Access flow <500 mL/min without clinical indicators of flow dysfunction ^a	%	%	...
Vascular access thrombosis	%	%	...
New vascular access	%	%	...
Non-maturation	%	%	...
Central venous catheter dysfunction	%	%	...
Unused vascular access	%	%	...
Other than flow dysfunction	%	%	...
High flow	%	%	...
Central vein obstruction	%	%	...
Hand ischemia	%	%	...
Vascular access (pseudo)aneurysm	%	%	...
Vascular access infection	%	%	...
New vascular access	%	%	...
Non-maturation	%	%	...
Central venous catheter dysfunction	%	%	...
Unused vascular access	%	%	...
Anesthesia			...
Local anesthesia	%	%	
Local anesthesia with sedation	%	%	
Locoregional anesthesia	%	%	
Regional anesthesia	%	%	
Hospital admission			...
Outpatient	%	%	
Day case	%	%	

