Multiple days	%	%	

^a Clinical indicators of flow dysfunction refer to the decision rules for interventions defined in the study protocol (used to send notifications to the study sites).

Statistical analysis: Chi squared test for categorical variables.

Major interventions are defined as interventions with general anesthesia and/or multiple day hospital admission.

Table 3C: Characteristics of percutaneous interventions

	All patients (N=...)		Monitoring (N=...)		Surveillance (N=...)	P
Stenosis		N		N		N
None	%	N	%	N	%	N
Single	%	N	%	N	%	N
Multiple	%	N	%	N	%	N
Stenosis characteristics ^a						
Location		N		N		N
Fistulas	%	N	%	N	%	N
Arterial inflow	%	N	%	N	%	N
Juxta-anastomotic vein	%	N	%	N	%	N
Outflow vein ^b	%	N	%	N	%	N
Central vein	%	N	%	N	%	N
Graft	%	N	%	N	%	N
Arterial inflow	%	N	%	N	%	N
Juxta-anastomotic arterial	%	N	%	N	%	N
In graft	%	N	%	N	%	N
Juxta-anastomotic venous	%	N	%	N	%	N
Outflow vein	%	N	%	N	%	N
Central vein	%	N	%	N	%	N
Vessel preparation						
Balloon type						...
Standard balloon	%		%		%	
High pressure balloon	%		%		%	
Cutting balloon	%		%		%	
Balloon diameter (mm)	... + SD	N	... + SD	N	... + SD	N
Balloon inflation time (min)	... + SD	N	... + SD	N	... + SD	N
Balloon inflation pressure (atm)	... + SD	N	... + SD	N	... + SD	N
Additional treatment						
Paclitaxel-coated balloon	%		%		%	...
Paclitaxel-coated balloon diameter (mm)	... + SD	N	... + SD	N	... + SD	N
Stent	%	N	%	N	%	N
Covera	%	N	%	N	%	N
Viabahn	%	N	%	N	%	N
Wrapsody	%	N	%	N	%	N
Supera	%	N	%	N	%	N
Stent diameter (mm)	... + SD	N	... + SD	N	... + SD	N
Stent length (mm)	... + SD	N	... + SD	N	... + SD	N
Treatment effect						
Subjective assessment						
Luminal loss before treatment (%)	... + SD	N	... + SD	N	... + SD	N
Luminal loss after treatment (%)	... + SD	N	... + SD	N	... + SD	N
Core lab assessment						
Luminal loss before treatment (%)	... + SD	N	... + SD	N	... + SD	N
Luminal loss after treatment (%)	... + SD	N	... + SD	N	... + SD	N

^a For multiple stenoses, the most severe stenosis (i.e. highest PSV-ratio with duplex ultrasound) is chosen.

^b Outflow vein may be subdivided into cannulation zone / outflow vein / cephalic arch / swing segment when angiography images are available.

Statistical analysis: Chi squared tests for categorical variables and Student t-test for continuous variables

Table 3D: Complications of percutaneous interventions

	All patients (N=...)		Monitoring (N=...)		Surveillance (N=...)		P
No complications	%	N	%	N	%	N	...

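### Table 3B compares indications for intervention as shares of a total that the trial is sized to change, and symptomatic versus flow-only interventions have no rate comparison anywhere else

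*SAP*

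**What the plan says.** SAP section 5.1.1 sets the endpoint: "The primary outcome will be defined as the number of interventions required for each patient-year of hemodialysis treatment". Section 2.3 sizes the trial on that count: "we aim to detect a difference in the intervention rate of 0.25 per year between study groups".

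In section 6, "Table 3B: Characteristics of vascular access interventions" has one column per group headed by an N, percentages in the cells and a P column. The note beneath reads "Statistical analysis: Chi squared test for categorical variables". The shell has no patient-years and no rate ratio. Section 3.1 treats P below 0.05 as significant unless the SAP states otherwise, and nothing marks Table 3B as descriptive.

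Other shells use time at risk. Tables 3A and 4A to 4C have patient-year columns and event rate ratios. Table 2M does the same with person-years and separates examinations prompted by clinical indicators from those prompted by low flow alone, but it counts duplex examinations, not interventions. Section 3.2.1 makes low flow alone an indication in the control group only.

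**The concern.** The denominator in Table 3B is a count that arises after randomization and that the allocated strategy is meant to change. If monitoring removes interventions prompted by low flow alone and nothing else changes, every remaining indication takes a larger share of a smaller total, although patients undergo it no more often. A reader who sees a significant P value beside the symptomatic row may conclude that dropping surveillance produced more symptomatic interventions.

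That question matters to this trial. Its objective is to learn whether surveillance can be abandoned safely, and a natural follow-up is whether the flow-prompted interventions disappear or return as symptomatic ones. For symptomatic interventions, Table 3B is the only place where the groups are compared, and shares cannot answer the question.

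A second weakness is that the chi-squared test treats every intervention as independent, whereas the Table 3A model has a random intercept per participant because patients have repeated interventions.

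**Working it through.** **Inputs from the SAP (section 2.3).** Control rate: "these figures amount to an average of 1.77 interventions per patient-year in the Netherlands". Planned difference 0.25, so 1.52 under monitoring. Follow-up: "A total follow-up time of 828 patient-years (414 patient-years in each treatment arm) achieves 80% power". Test: "two-sided, large-samples z-test of the Poisson event-rate difference at a significance level of 0.05".

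**Reproducing the plan's own figure.** Patient-years per arm = (1.960 + 0.842)² × (1.77 + 1.52) / 0.25² = 7.849 × 3.29 / 0.0625 = 413.2, rounded up to 414. Power at 414 is 80.1%. The figure reproduces. (Weighting 1.56 and 3.30 by 8:1 gives 1.753 rather than 1.77. This does not affect the point, and 1.77 is kept.)

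**Input not in the SAP.** The rate of each indication. I assume a common rate r per patient-year, equal in both groups, and vary it from 0.1 to 1.25.

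**Shares.** Expected interventions are 414 × 1.77 = 733 under surveillance and 414 × 1.52 = 629 under monitoring. The shares are r/1.77 and r/1.52. Their ratio is 1.77/1.52 = 1.16 whatever r is.

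**Chance of a significant result.** The approximate power of the chi-squared test is Φ(d/SE − 1.96), where d is the difference in shares and SE = √[p(1 − p)(1/629 + 1/733)] with p the pooled share. For r = 0.3: d = 0.197 − 0.169 = 0.028, p = 248.4/1362 = 0.182, SE = 0.021, d/SE = 1.33 and Φ(−0.63) = 0.26. For r = 1.0: d = 0.658 − 0.565 = 0.093, p = 828/1362 = 0.608, SE = 0.0265, d/SE = 3.50 and Φ(1.54) = 0.94. Simulation with independent Poisson counts, 40,000 trials per row, agrees:

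| Assumed equal rate per patient-year | Surveillance share | Monitoring share | Monitoring significantly higher |
|---|---|---|---|
| 0.1 | 5.6% | 6.6% | 11% |
| 0.2 | 11.3% | 13.2% | 18% |
| 0.3 | 16.9% | 19.7% | 26% |
| 0.5 | 28.2% | 32.9% | 46% |
| 0.75 | 42.4% | 49.3% | 73% |
| 1.0 | 56.5% | 65.8% | 94% |
| 1.25 | 70.6% | 82.2% | over 99% |

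**Sensitivity to the total.** If the true reduction were 0.5 per year, twice the planned difference, the probability would be 35% at r = 0.1, 83% at 0.3 and 98% at 0.5. If the totals do not differ, monitoring is significantly higher in about 2.4% of trials at r = 0.3, which is what chance alone gives.

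**Same data on patient-years.** Equal rates give a rate ratio of 1.00, and a two-sided rate test rejects in 4.8 to 5.2% of trials at the planned difference.

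**The opposite direction.** Shares can also hide an increase. If thrombosis-indicated interventions rose from 0.30 to 0.35 per patient-year while the total rose from 1.77 to 2.07, the shares would be 0.30/1.77 and 0.35/2.07, both 16.9%.

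All these probabilities treat interventions as independent, as the chi-squared test does. Clustering within patients is not included.

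**The case against.** The strongest reply is that the chi-squared test is answering a different question. It asks whether the mix of indications among performed interventions is the same in both groups. In the scenarios above the mix does differ, so a rejection is correct for that hypothesis and is not an inflated type I error. This stands, apart from the clustering. The fault is that a share with a P value invites reading as a frequency.

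A reader might also infer that equal thrombosis rates will show up as significantly higher under monitoring. The documents do not support that. It requires a lower monitoring total, and for an assumed thrombosis rate of 0.1 to 0.5 per patient-year the chance is 11 to 46% at the planned effect. Thrombosis is moreover a secondary outcome per person-year with its own rate ratio in Table 4A, and thrombectomies have rate ratios in Table 3A. There, Table 3B would sit beside a correct analysis, not replace it.

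Nor is it right that no table gives any rate by reason for intervention: Table 3A separates procedures for flow dysfunction from other access procedures. It does not split the former into symptomatic and flow-only. Crude rates could be recovered from Table 3B's N and percentages with Table 3A's patient-years, but an interval that respects repeated interventions could not.

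Finally, modelling every row would be excessive. Many sub-rows will be sparse, and anesthesia and admission are natural descriptors of a procedure. That is accepted, and the fix is limited accordingly.

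**Conclusion.** The point holds in a limited form. Table 3B's P values do not compare how often each indication occurs. At the planned effect they favour a higher monitoring share by a factor of 1.16 for any indication with equal rates. The practical effect ranges from small for rare indications to near certain for those at about 1 per patient-year or more, and it vanishes if the totals are equal. The uncovered question is the rate of symptomatic versus flow-only interventions by group.

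This rests on assumed indication rates, on independent Poisson counts, and on reading N as interventions, which follows from the table's title because the header does not define it. A reader might infer that the primary result is compromised. It is not: the primary outcome is analysed as a rate, and indication mix is not among the outcomes listed in section 5.1.

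**What to change.** In Table 3B, for the four main indication rows (clinical indicators of flow dysfunction; flow below 500 mL/min without such indicators; thrombosis; reasons other than flow dysfunction), give the number of interventions per patient-year by group with a rate ratio and 95% CI, in the format of Tables 2M and 3A. Use the model with a participant random intercept, in whatever form is settled for the primary analysis. Its present description combines an identity link with an exponentiated coefficient, which should be resolved there first.

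The flow-only row should be near zero under monitoring by design. Give counts and rates only if a ratio cannot be estimated.

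Keep the percentages for the sub-rows and for anesthesia and admission as description, without P values, and define N in the header as interventions.

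The cost is a table-shell edit and a few extra model fits. No new data are needed.
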